## **Aim**

To prospectively compare the incidence of biliary complications after liver transplantation in patients who are randomized to undergo biliary reconstruction with and without biliary stents.

## **Secondary Aim**

To retrospectively evaluate the incidence of biliary complications after liver transplantation in non-randomized patients who undergo biliary reconstruction with or without biliary stents in the same time period.

## **Background**

Despite tremendous advances in other areas of orthotopic liver transplantation, biliary reconstruction remains a major hurdle. Morbidity related to biliary complications has been estimated to be as high as 30%. The risk of biliary complications can be related to the type of transplant performed and the technique used for reconstruction of the bile duct. One of the main techniques of performing biliary reconstruction is a choledochocholedochostomy which can be performed over an anastomotic stent.

Although placement of biliary stents is routine practice in many liver transplant centers around the country, there is no evidence to support their use. As of now both the placement and non-placement of a stent are essentially “standard of care. What has been extensively studied in the literature is the use T-tubes. In the early years of liver transplant, T-tubes were touted as a great mechanism to prevent anastomotic biliary strictures. However, their unanimous use is no longer supported as several retrospective and prospective studies have shown that their routine use led to more biliary complications including bile leaks, cholangitis, displacement of the tube, and bile duct obstruction. Although, biliary stricture formation may have been prevented, the rate of biliary complications did not offset this benefit. This was largely due to the fact that a T-tube created an additional defect in the bile duct wall. Given these findings, in the 1990s, many transplant centers started performing biliary reconstruction without the use of T-tubes.

In our center, many of our transplant surgeons now perform the biliary anastomosis over a pediatric feeding tube which is used as a stent. The hope is that use of these internal stents will help prevent post-operative biliary strictures without the added risk of biliary complications seen with T-tubes. It is expected that the stent will migrate out on its own in the early days/weeks after a transplant. However, the practice of using stents in biliary anastomosis is not uniform and there are no established guidelines to support their indiscriminate application. We have designed a prospective randomized trial to evaluate the effect of stent placement on biliary complications and its effect on morbidity.

## **Study Design**

A randomized prospective study will be conducted of patients at Vanderbilt University Medical Center (VUMC) who undergo liver transplantation from March 1st, 2014 until approximately 120 patients are randomized. We will simultaneously perform a review of patients at VUMC who undergo liver transplantation but cannot be randomized for logistical reasons (i.e. hepatic encephalopathy, timing of the transplant procedure, or

language barriers). Data from the two groups will be evaluated independently and comparatively. The inclusion of both groups of data is critical to avoid bias in the findings due to inadvertent selection of patients who may not have the same risk for biliary complications. All data will be de-identified and stored using a secure database, REDCap.

## **Inclusion Criteria**

- 18 years and older
- Have received a deceased full size liver graft
- Need for hepaticojejunostomies or reduced size grafts

## **Recruitment**

Informed consent will be sought from new patients undergoing evaluation from liver transplant during their clinic visit with the transplant surgeon. For those patients currently on the waitlist for transplant, who have already undergone evaluation, consent will be sought during their subsequent upcoming clinic visits before transplant. We will also seek out patients who are currently hospitalized and are on the liver transplant waitlist. Lastly, for those patients with no clinic visits in the near future but for whom transplant is imminent, we will reach out to them at their preferred contact number to discuss the proposed project and seek informed consent.

Due to timing of the liver transplant procedure or the ability of the patient to understand the informed consent document, some patients may not be able to provide informed consent and will not qualify for randomization. Use of a stent in these patients will be determined at the discretion of the surgeon. A retrospective review of the data for these patients will be conducted.

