## **Surgical Procedure**

The surgical procedures are standardized. The operation will be performed exclusively by

5 hepatobiliary surgery attendings, each with individual experience of over 100 liver transplantations.

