### **Statistical Analysis**

The probability of being free of a biliary complication and the probability of liver graft survival will be estimated by the Kaplan Meier method. Continuous variables will be analyzed using Student's t test, or Wilcoxon's rank sum test. Categorical variables will be analyzed using Chi-square test or Fisher's exact test. Multivariable proportional hazards regression will be performed to adjust potential confounders. A P value of <0.05 will be considered statistically significant.

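### Secondary aim: surgeons choose the stent outside the randomisation, but operating surgeon is not recorded, listed as a confounder or used in the analysis, so the comparison may be confounded by surgeon and its P values too small

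*Combined protocol and SAP*

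**What the plan says.** The Secondary Aim is "To retrospectively evaluate the incidence of biliary complications after liver transplantation in non-randomized patients", with or without stents, over the same period as the trial. Recruitment explains how those patients come to have a stent or not: "Use of a stent in these patients will be determined at the discretion of the surgeon". No patient criterion for stenting is given.

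Two sections bear on how that choice may fall. The Background says that "many of our transplant surgeons now perform the biliary anastomosis over a pediatric feeding tube which is used as a stent" and that "the practice of using stents in biliary anastomosis is not uniform". Surgical Procedure says the operations are done only by "5 hepatobiliary surgery attendings, each with individual experience of over 100 liver transplantations", and also that "The surgical procedures are standardized".

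The analysis section does not separate the two cohorts. It says "Categorical variables will be analyzed using Chi-square test" or Fisher's exact test, and adds t or rank-sum tests, Kaplan-Meier estimates and a multivariable proportional hazards model, all judged at P<0.05. No surgeon stratum, random effect or clustered variance is mentioned. Surgeon is not among the confounders named under Limitations, and the Appendix 1 data sheet has a field for stent placement but none for the operating surgeon.

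**The concern.** In the randomised cohort a sealed envelope decides on the stent. In the other cohort the surgeon decides. If some surgeons usually stent and others usually do not, stented and unstented patients are largely patients of different surgeons. Any difference in complication rates between those surgeons then appears as a stent effect. For this particular set of surgeons that is confounding, and it shifts the estimate. Seen over repeated sets of surgeons, it is extra variation that the patient-level tests leave out, so P<0.05 occurs more often than 5% of the time when the stent does nothing. Balance on patient risk factors does not remove it.

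Study Design says the randomised and non-randomised data will be looked at both separately and against each other. A surgeon difference read as a stent effect would therefore sit beside the trial result and seem to confirm or contradict it. With no surgeon field on the data sheet, the data set as specified could not be used to check.

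**Working it through.** **Plan's own figure.** There is none to reproduce. The documents give no cohort size, per-surgeon stent rate or between-surgeon variation for the secondary aim.

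**Inputs from the documents.** Five surgeons (Surgical Procedure). An upper figure of 30% for biliary morbidity (Background). Alpha 0.05 (Statistical Analysis; two-sided assumed).

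**Assumed inputs.**
- Cohort of 60 or 120, so m = 12 or 24 patients per surgeon at equal volume.
- Complication risk p = 30% or 15%, with no true stent effect.
- Between-surgeon SD 0.3 or 0.5 on the logit scale. At 30%, one SD either side is 24-37% or 21-41%.
- Three habitual stenters and two non-stenters, who follow their habit 100%, 90% or 75% of the time.

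**Step 1: clustering of the outcome.** ICC(outcome) ≈ p(1-p) × SD².
- At 30%: 0.21 × 0.09 = 0.019 and 0.21 × 0.25 = 0.053.
- At 15%: 0.1275 × 0.09 = 0.011 and 0.1275 × 0.25 = 0.032.

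**Step 2: clustering of stent use.** ICC(stent) = variance of the surgeons' stent rates / [mean × (1 - mean)].
- 100% habit: 1.
- 90% habit: mean 0.58; 0.1536/0.2436 = 0.63.
- 75% habit: mean 0.55; 0.06/0.2475 = 0.24.

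**Step 3: false-positive rate.** Design effect DE = 1 + (m-1) × ICC(outcome) × ICC(stent). Actual error = 2 × [1 - Φ(1.96/√DE)].

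Worked case (30%, n=120, SD 0.5, 100% habit): DE = 1 + 23 × 0.0525 × 1 = 2.21; 1.96/√2.21 = 1.32; error 0.187. A simulation of the same setting (8,000 replicates, Pearson chi-square) gives 0.185.

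At 30% risk, formula / simulation:

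| Habit | n=60, SD 0.3 | n=60, SD 0.5 | n=120, SD 0.3 | n=120, SD 0.5 |
|---|---|---|---|---|
| 100% | 0.075 / 0.072 | 0.119 / 0.113 | 0.102 / 0.096 | 0.187 / 0.185 |
| 90% | 0.065 / 0.068 | 0.093 / 0.092 | 0.083 / 0.086 | 0.140 / 0.143 |
| 75% | 0.056 / 0.058 | 0.066 / 0.072 | 0.062 / 0.063 | 0.085 / 0.083 |

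At 15% risk the inflation is smaller. For n=120 and 90% habit, the formula gives 0.070 and 0.105 and simulation gives 0.071 and 0.107.

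**Step 4: when nothing happens.** DE is 1 and the error is 0.05 if ICC(outcome) = 0 (surgeons do not differ in risk) or ICC(stent) = 0 (all stent at the same rate). Simulation agrees. With every surgeon stenting half the time and n=120, the error is 0.048-0.052 for outcome ICCs of 0.01 to 0.10.

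**Step 5: does stratifying work, and what does it cost?** Mantel-Haenszel stratified by surgeon holds about 0.05 in the 90% and 75% settings (simulated 0.047-0.052). The share of information left is roughly 1 - ICC(stent): 0.37 at 90% habit and 0.76 at 75%. In simulation, with small strata, it is about 0.35 and 0.7. At 100% habit no within-surgeon comparison exists and the test cannot be computed.

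**The case against.** The case against has real force on several points.

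- **Nothing shows that surgeons differ in risk.** The protocol says "The surgical procedures are standardized" and that every operator is experienced, which points to small differences. Discretion also fits a patient-by-patient choice as well as a fixed habit. This stands: a reader might infer that the secondary-aim P values are certainly too small, and the documents do not support that. Non-uniform practice among surgeons makes differing stent use plausible; differing risk is neither shown nor ruled out.
- **Five surgeons do not mean five observations.** A reader might infer that the cohort is worth about five independent units. The largest design effect above is 2.21, so 120 patients are worth about 120/2.21 = 54, and at n=60 it is 1.58, so 60 are worth about 38.
- **The size rests on assumptions.** The 30% is an upper figure, the other inputs are assumed, and only the chi-square was simulated. Fisher's exact test is conservative in small tables, and the adjusted hazards model was not tried. This stands, which is why the result is a range.
- **The lists may be open.** Limitations introduces its confounders as inclusions, and the data sheet also omits donor age, which Limitations names. So surgeon could be added without contradicting the plan. That is true, but as written nothing commits the team to collect it.
- **The target analysis is inferred.** The Secondary Aim speaks of evaluating incidence, no test is tied to it, and no confidence intervals are mentioned. However, it concerns patients "in non-randomized patients who undergo biliary reconstruction with or without biliary stents in the same time period", and the only tests listed are patient-level ones.
- **Coverage of the five surgeons.** Surgical Procedure does not expressly include the non-randomised patients. The same centre and period make it likely.

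**Conclusion.** The gap is real and confined to the secondary aim. The surgeon chooses the stent, practice at the centre varies, as far as the documents show five surgeons operate, and the plan neither records surgeon nor allows for it. If stent use and complication risk both differ between surgeons, the comparison is confounded by surgeon and its P values are likely too small, by an unknown amount. Over the assumed ranges above, the chi-square false-positive rate runs from about 6% (barely above 5% in the mildest settings) to about 18%. If surgeons are alike in either respect, it is 5%.

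A reader might also extend this to the primary comparison. The documents do not support that: allocation is by envelope, opened just before the anastomosis, so a surgeon's preference does not determine the arm. The point therefore does not threaten the trial's main result. It does matter for how much weight the second cohort can carry beside it.

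**What to change.** 1. Add a coded operating-surgeon field (1 to 5) to the Appendix 1 data sheet, and add surgeon to the confounders under Limitations.
2. For the non-randomised cohort, tabulate stent use and complications by surgeon before any test.
3. For the secondary aim, replace the unstratified tests with within-surgeon comparisons: Mantel-Haenszel stratified by surgeon for incidence, and surgeon as a stratum in the proportional hazards model. Cluster-robust standard errors are not a good substitute, as they are unreliable with five clusters.
4. State in advance that if few surgeons use both methods, this cohort will be reported descriptively by surgeon, with no P value for stent.

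The cost is one data field and a few sentences of analysis text. The price is precision: the interval widens (about 35% of the information remains at 90% habit, about 70% at 75%), or the result becomes descriptive if surgeons do not overlap. Surgeons' choice of stent and the randomised analysis are left as they are.

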## **Randomization**

Patients will be prospectively randomized to 2 groups.

- Group 1 will undergo biliary reconstruction with stent placement at the anastomosis site.
- Group 2 will undergo biliary reconstruction without stent placement.

Randomization will be performed with sealed envelopes before liver transplantation. The envelope will be opened during the operation and the randomization arm will be revealed to the surgeon immediately prior to the start of the biliary anastomoses.

## **Surgical Procedure**

The surgical procedures are standardized. The operation will be performed exclusively by

5 hepatobiliary surgery attendings, each with individual experience of over 100 liver transplantations.

### **Follow-up Procedure**

The patient will be followed up per standard of care for their liver transplant.

If they were randomized to receive a stent placement, they will undergo an abdominal x-ray about 3 months after transplant. This x-ray is to see if the stent has been retained in the bile duct or if it needs to be extracted by an endoscopic procedure. This abdominal x-ray is standard of care.

### **Outcome**

Our primary outcome of interest is biliary complications. We will compare the incidence of biliary strictures, biliary leaks, cholangitis, and stones between the group that receives biliary stents and the group that does not. We will determine the time interval between transplantation to the occurrence of a complication. We will collect data on reoperations, conversion to hepaticojjunostomies, performance of an endoscopic retrograde cholangiopancreatography (ERCP) and additional hospital days incurred as a result of the biliary complication.

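### Does the plan leave open whether a retained stent counts as a biliary complication?

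*Combined protocol and SAP*

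**What the plan says.** Under Outcome, the primary outcome is biliary complications, and the next sentence lists what will be compared: "We will compare the incidence of biliary strictures, biliary leaks, cholangitis, and stones". The list has four entries and no wording that leaves room for others. The section then adds time to a complication, and reoperation, conversion, ERCP and hospital days that result from one.

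Statistical Analysis estimates "The probability of being free of a biliary complication" by Kaplan-Meier and gives general tests for categorical and continuous variables. It does not restate what a complication is.

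Follow-up Procedure describes a check made in one arm only: "If they were randomized to receive a stent placement, they will undergo an abdominal x-ray about 3 months after transplant". Its purpose is to find a retained stent that may need endoscopic removal. The Data Sheet (Appendix 1) has items for retained stent, the extraction procedure, its cost and its complications.

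The Background says of T-tubes that "their routine use led to more biliary complications including bile leaks, cholangitis, displacement of the tube, and bile duct obstruction". It hopes that internal stents will "help prevent post-operative biliary strictures without the added risk of biliary complications seen with T-tubes", and of the stent used here it says: "It is expected that the stent will migrate out on its own in the early days/weeks after a transplant".

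**The concern.** The Background counts a device event, displacement of the tube, among biliary complications, and it frames the trial's hope in the same term. The Outcome list contains no device event. Statistical Analysis and the Data Sheet then refer to a biliary complication without repeating a definition. A reader could conclude that the plan leaves it open whether a retained stent is a primary event.

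The stake is real in principle. Retention can occur only in a patient with a stent, and the x-ray that looks for it is scheduled only for the stent arm, so counting it adds events to one side. The surgeon learns the allocation in theatre and no blinded outcome assessment is described, so a classification made late could be made with the arm and the results known. If retention is left out and nothing is said about extraction, a report of fewer complications with stents might not show the extra procedures that stents led to.

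**Working it through.** **Step 1. What defines the endpoint.**

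| Section | Subject | Bearing on this trial's endpoint |
|---|---|---|
| Outcome | This trial's comparison | Four named events, closed list |
| Statistical Analysis | Freedom from a biliary complication | Takes its meaning from Outcome |
| Background | T-tubes in earlier studies | Describes another device; defines nothing here |
| Follow-up Procedure | x-ray for retention | A check on the stent, not an outcome definition |
| Data Sheet | Items to record | Retention and extraction are collected |

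The Background attributes the T-tube excess largely to the extra hole the tube makes in the duct wall, which has nothing to do with retention. Displacement is not retention: this stent is expected to pass out by itself, and retention is the failure to do so. Duct obstruction, also on the T-tube list, overlaps with the strictures and stones already named under Outcome. The Background therefore supplies no second definition that competes with the Outcome list. The indentation of the Data Sheet is lost in the text available, so nothing is inferred from where the retained-stent item stands.

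**Step 2. How far apart the two codings are.** The plan has no figure to reproduce here: the number randomised is given ("until approximately 120 patients are randomized") without power, effect size or a design event rate.

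Inputs:
- 120 randomised (Study Design); equal split assumed, so 60 per arm.
- Significance at p<0.05 (Statistical Analysis); two-sided assumed.
- Control event rate 30%, the upper Background figure ("Morbidity related to biliary complications has been estimated to be as high as 30" per cent); 20% is an assumed alternative.
- Stent-arm rate equal to control, or 15% (assumed).
- Retention r of 2% to 20% (assumed; no rate is given), independent of the listed events.

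If retention counts, the stent-arm rate becomes q = 1 − (1 − p)(1 − r). With p = 30% and r = 5%, q = 1 − 0.70 × 0.95 = 33.5%, or 60 × 0.035 = 2.1 extra patients. With p = 15% and r = 10%, q = 1 − 0.85 × 0.90 = 23.5%, or 60 × 0.085 = 5.1 extra patients.

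Exact enumeration: X ~ Bin(60, stent rate), R ~ Bin(60 − X, r), Y ~ Bin(60, control rate). One coding compares X with Y, the other X + R with Y. The table gives the chance that the verdicts (stent better, no difference, stent worse) differ, by uncorrected chi-square, with Fisher's exact test in brackets.

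| Stent v control | r = 2% | r = 5% | r = 10% | r = 20% |
|---|---|---|---|---|
| 20% v 20% | 2.6% (1.6) | 7.1% (4.5) | 17.7% (12.3) | 51.0% (42.0) |
| 30% v 30% | 2.0% (1.3) | 5.3% (3.5) | 12.4% (8.6) | 35.6% (28.5) |
| 15% v 30% | 10.0% (9.4) | 23.2% (21.0) | 38.9% (33.3) | 54.3% (43.7) |

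For 15% v 30%, the chi-square chance of finding the stent better is 51.4% on the four events. It is 41.5%, 28.3%, 12.8% and 1.5% if retention counts, at the four values of r.

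**Step 3. A single trial at the expected counts.** For 15% v 30% these are 9 and 18 events. The pooled rate is 27/120 = 0.225, and z = 0.15 / √(0.225 × 0.775 × 2/60) = 1.97, p = 0.049. With one patient recoded, 10 v 18: pooled rate 28/120 = 0.233, z = 0.133 / √(0.233 × 0.767 × 2/60) = 1.73, p = 0.084. Fisher's test, which the plan also allows, gives 0.079 and 0.130, so under that test nothing flips.

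**Step 4. What the figures show.** They show that a four-event endpoint and one that includes retention are different endpoints. They do not show that the plan fails to choose: by Step 1, it names four events.

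**The case for a change.** The strongest case for a change does not need the Background at all. Even if the four-event list is final, neither Outcome nor Statistical Analysis says how retention, extraction and complications of extraction will be reported. ERCP is listed only where it results from a biliary complication, so an endoscopic removal of an otherwise harmless retained stent has no obvious place. Outcome assessors are not said to be blinded, one sentence would settle the matter, and the table shows that the coding can decide the verdict when stents work.

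Part of this stands. The plan has no sentence stating that retention alone is not a primary event, or how the stent items will be summarised. But the items are collected, and the general provision for categorical variables covers them as much as any other item, since the plan names no secondary variable individually. A patient without a stent cannot retain one, so the natural summary is a count and percentage in the stent arm, which any competent report would give.

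The large percentages in the table need retention rates that sit poorly with the expectation of spontaneous passage. In the 15% v 30% scenario the chance of a positive result is only about one in two before any recoding, so part of the fragility comes from the size of the trial. A formal between-arm test of a composite that includes stent events would also be debatable, because its stent-only part is necessarily zero in unstented patients.

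**Conclusion.** No change follows. The Outcome section names four events, and an analyst who follows it obtains a sound comparison of the same events in both arms. What is missing is a line of reporting detail that the collected data allow analysts to fill sensibly: primary event by the four-event list, with retention and extraction described for the stent arm.

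The gap between the codings runs from 1.3% (30% in both arms, 2% retention, Fisher) to 54.3% (15% v 30%, 20% retention, chi-square). All of these figures rest on assumed retention rates, an assumed equal split and, apart from the 30%, event rates that the documents do not give. They illustrate why one would not want to switch endpoints after seeing the results. They are not evidence that the plan invites it.
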